6.1.2 Exclusion Criteria

The following patients will not be included in this observational study:

- Patients who are not covered in the latest version of the HUMIRA syringe[®] SPC and HUMIRA Pen[®] SPC;
- Patients participating in another study program or clinical trial.
- Patients who have been treated with Adalimumab before.-

6.2 Number of patients to be enrolled

It is planned to enroll approximately 140 patients in total (80 RA, PsA and AS / 30 PsO /30 MCeor UC). The study will be conducted at 28 sites in Austria. Each site shall enroll approximately 5 patients.

6.3 Investigator Selection Criteria

The investigational sites will be centers with experience in the treatment of RA, PsA, AS, PsO, CD and UC patients. For the investigators it is not mandatory to have any clinical research (i.e. PMOS) experience but it may be beneficial.

6.4 Study Duration

This PMOS has started In RA, PsA and AS in Feb 2013. The study start for PsO, CD and UC was in November 2014. The estimated end of the patient inclusion is September 2016. Each patient will be observed for a period of max.12 months. Follow-up of patients should enable approximately 5 patient visits (including screening = visit 1) during 12 months. For these reasons, the most likely visits are defined as "V1", "V2", "V3", "V4" and "V5" although numbers

Confidential Information No use or disclosure outside AbbVie is permitted without prior written authorization from AbbVie

and dates will depend only on the decision of the physician. A schedule of activities can be found in the next section. According to the standard of care the approximate frequency of the visits will be 3 months. As a result, failure to meet these suggested dates will not constitute a breach of the protocol.

6.5 Study Conduct and Schedule of Activities:

The study will be conducted in a prospective, single-country, multicenter format. The participating investigator will provide the patient with a prescription for HUMIRA[®]40mg syringe or HUMIRA[®]40mg pen, as the patient can select between two available application devices. Depending on a patient's selection, the investigator will also provide him/her the instructions for appropriate use of the HUMIRA[®]40mg pen (please see Appendix-A) or HUMIRA[®]40mg syringe (please see Appendix-B). Patient safety data and information about co-medications other medications or supplements taken for RA, PsA, AS, PsO, CD or UC will be recorded on electronic data report forms (eCRFs) at study enrollment and during their regularly scheduled visits. If treatment with Adalimumab is interrupted, standard practice is to review the patient after a period of 3 months. If the physician decides to permanently discontinue Adalimumabbefore the end of the planned observational period of 12 months, the reason for discontinuation and the new RA, PsA,AS, PsO, CD or UC treatment regimen prescribed, if applicable, will be documented. The next routine follow-up visit will be the termination visit for this patient in the post-marketing observational study.

There is no recommendation regarding an appropriate amount of time for wash out of previous BDMARDs prior to initiating Adalimumab therapy. The determination of an appropriate time to initiate Adalimumab following discontinuation of another BDMARD is at the discretion of the physician. While individual patient variability can affect drug elimination, it is generally felt that a majority of a drug is eliminated after 4 to 5 drug half-lives. The health care professional may wish to consider this in determining the appropriate time to initiate Adalimumab therapy. Health care providers should use their knowledge of TNF α biology and best clinical judgment when determining an appropriate washout period of previous BDMARD therapy. AbbVie Austria's recommended wash out periods are: Etanercept received > 3 weeks (21 days) before 1st

_ 10

Adalimumab application Infliximab received > 8 weeks (56 days) before 1st Adalimumab

application

Schedule of Activities

ACTIVITIES	VISIT 1	VISIT 2	VISIT 3	VISIT 4	VISIT 5	EARLY
	SREENING					TERMI-
						NATION
TIME	Month 0	Month 3	Month 6	Month 9	Month 12	
Inclusion /Exclusion Criteria	x		57			
Written authorization to use data	X					
Patient demographics ^a	x		2			
TB: Chest X-ray	x					
TB: IGRA test	x		3			
TB: PPD skin test ¹	х					
ESR	x	x	X	X	X	x
CRP	X	X	X	X	X	х
RADAI ^c	x	x	x	x	x	x
BASDAI ^d	x	x	x	x	x	x
PASI ^e	x	x	x	X	x	x
Harvey-Bradshaw Index (HBI) ^f	x	x	x	x	x	x
Partial Mayo Score ^g	x	x	x	x	x	x
Beliefs about Medicines Questionnaire (BMQ)	x				×	x
Morisky Medication Adherence Scale (MMAS)		x	x	X	x	x
Treatment Satisfaction Questionnaire for Medication (TSQM)		x	x	x	x	x
Concomitant treatment	x	X	X	X	X	x
Adalimumabapplication ^b	x	X	x	x	X	x
Final Statement ^h					X	x

a. Patient demographics: year of birth, gender, race, disease, duration of RA,PsA,AS and previous as well as concomitant treatment

b. Adalimumabadministration: at screening information about dosing frequency and date of first as well as any further applications.

c. for RA and if reasonable for PsA, only

- d. for patients with AS only
- e. for patients with PsO only
- f. for patients with CD only
- g. for patients with UC only

Confidential Information

No use or disclosure outside AbbVie is permitted without prior written authorization from AbbVie

_ 11

abbvie

Adalimumab P13-562 Protocol

- h. Final statement shall also include a statement about pain-management with respect to a potential influence of adalimumab
- According to the recommendations of the German central committee for the fight against tuberculosis all patients who are about to be treated with a TNF-inhibitor should be screened for a latent tuberculosis infection by the use of a highly specific interferon-γ-test (IGRA interferon gamma release assay) in addition to chest X-ray and an accurate careful anamnesis.

Please see also APPENDIX C !

AUSTRIAN CONSENSUS STATEMENT ABOUT TUBERCULOSIS & BIOLOGICALS

RECOMMENDATIONS FOR TUBERCULOSIS SCREENING BEFORE INITIATION OF TNFα-INHIBITOR TREATMENT IN RHEUMATIC DISEASES

As by the use of the PPD skin test (Mendel Mantoux) false positive or false negative test results are expected in patients with latent tuberculosis, the PPD skin test shall be used in exceptional cases only.

The PPD-skin test as a supplementary test is useful only in the following cases, if:

- in spite of a negative IGRA test an earlier tight exposure to a patient with infectious lung TB is anamnestic plausible
- a BCG (Bacille Calmette-Guérin) vaccination in due consideration of the immunisation policy of the respective country of origin of a patient is implausible and/or
- a IGRA-test is indeterminable in the repetition
- In such cases a positive PPD test defines the further course of action.

If a patient has had a PPD test placed within 3 months prior to the first Adalimumab-application, a repetition of the PPD test

will not be required provided the following conditions are met:

- 1. There is documentation signed by a licensed health care professional that the PPD test was read within 48-72 hours of placement and a precise assessment of induration in millimetres is included.
- 2. The chest x-ray before first Adalimumab-application does not indicate any evidence of TB (no evidence of calcified granulomas, no evidence of pleural scarring and no evidence of latent TB)
- 3. Nothing in the patient's history has changed since the time of the PPD tests to warrant a repeat test.

Please see also APPENDIX C! CDC Treatment Recommendations for Positive PPD; CDC CENTERS FOR DISEASE CONTROL AND PREVENTION

6.5.1 Description of Activities

Beliefs about Medicines Questionnaire (BMQ)

The BMQ is a method for assessing cognitive representations of medication. The questionnaire comprises two sections: the BMQ-Specific which assesses representations of medication prescribed for personal use and the BMQ-General which assesses beliefs about medicines in general. The BMQ-Specific comprises two 5-item factors assessing beliefs about the necessity of prescribed medication (Specific-Necessity) and concerns about prescribed medication based on beliefs about the danger of dependence and long-term toxicity and the disruptive effects of medication (Specific-Concern). The BMQ-General comprises two 4-item factors assessing beliefs that medicines are harmful, addictive, poisons which should not be taken continuously (General-Harm) and that medicines are overused by doctors (General-Overcure). The total

score, the sum of all the points from the Specific AND General questions range from 17 (lowest score) to 85 (highest score). Patients who have positive beliefs about medicine have a score < 47 and patients who have negative beliefs have a score > 47.

Morisky Medication Adherence Scale (MMAS)

The MMAS is a 4-item Self-Report Measure of Medication-Taking Behavior. It measures both intentional and non-intentional non-adherence (based on forgetting, carelessness, stopping medication when feeling better, or stopping medication when feeling worse). The 4-item MMAS-4-item consists of 4 questions which can be answered with yes (=0 point) and no (=1 point). The MMAS score is the sum of all four question and range from 0 (=non-adherent) to 4 (=adherent).

Treatment Satisfaction Questionaire for Medication (TSQM)

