5.0 Study Objectives

5.1 Main objectives

The main purpose of this study is to assess patients' adherence attitudes (beliefs) to the maintenance therapy with a scheduled Adalimumab monotherapy or a combination therapy with methotrexate and to investigate whether there are correlations between such beliefs and adherence to maintenance treatment. In order to measure such beliefs the following questionnaire is used:

 Changes in the Beliefs about Medicines Questionnaire (BMQ) at 12 months compared to baseline. In addition, the correlations between beliefs and adherence to treatment will be done at baseline and at 12 months

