11.2 Plan of Analysis

The statistical analysis shall describe the characteristics of patients included in the survey together with outcomes and clinical tolerability of Adalimumab.

Subject to the level of measurement of the respective variables appropriate descriptive statistics is used: e.g. frequency absolute and/or percental; nonmissing, missing data respectively; mean, standard deviation, where applicable: median, 25th percentile (first quartile) and 75th percentile (third quartile), minimum and maximum, range, calculation of confidence intervals (if applicable). Appropriate graphs are used (e.g. scatterplot, boxplot, histogram, etc.). As the study is an open label non-interventional post marketing observational study there is no working hypothesis allowed!

Compliance with treatments, outcomes and clinical tolerability of treatments will be compared as a function of patient characteristics.

A data analysis plan will be available prior to the conduct of the statistical analysis for the study.

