11.2.2 Reason for switch to HUMIRA[®]

Never achieved satisfactory response:	У	n
Achieved satisfactory response initially, but lost it over time:	у 🗌	n
Discontinued treatment due to intolerance/side effect(s) :	у 🗆	n

Others

HUMIRA (Adalimum: For each vi	ab)
ESR (mm / 1 hr) (Erythrocyte Sedimentation Rate)	CRP (mg/l) (C-Reactive Protein)

Confidential Information No use or disclosure outside AbbVie is permitted without prior written authorization from AbbVie

P13-562 Protocol

Adalimumab

For Visit 1, Visit 5, and as appropriate for Early Termination 10-item Beliefs about Medicines Questionnaire (BMQ)

We would like to ask you about your personal views about your medicine and medicine in general. Please circle how you feel about each of the statements. There is no right or wrong answer, we are interested in your personal views.

Score:1-5 1. My health, at present, depends on my medicines **Confidential Information** No use or disclosure outside AbbVie is permitted without prior written authorization from Version: 6.5; 27 Oct 2016 Page 79 of 110

a. Strongly disagree b. disagree c. uncertain d. agree e. strongly agree

- My life would be impossible without my medicines
 a. Strongly disagree b. disagree c. uncertain d. agree e. strongly agree
- Without my medicines I would become very sick
 a. Strongly disagree b. disagree c. uncertain d. agree e. strongly agree
- 4. My health in the future will depend on my medicines
 a. Strongly disagree b. disagree c. uncertain d. agree e. strongly agree
- My medicines protect me from becoming worse
 a. Strongly disagree b. disagree c. uncertain d. agree e. strongly agree
- Having to take medicines worries me
 a. Strongly disagree b. disagree c. uncertain d. agree e. strongly agree
- 7. I sometimes worry about the long term effects of my medicines
 a. Strongly disagree b. disagree c. uncertain d. agree e. strongly agree
- My medicines are a mystery to me
 a. Strongly disagree b. disagree c. uncertain d. agree e. strongly agree
- 9. My medicines disrupt my life
 a. Strongly disagree b. disagree c. uncertain d. agree e. strongly agree
- I sometimes worry about becoming too dependent on my medicines
 a. Strongly disagree b. disagree c. uncertain d. agree e. strongly agree

Total 10-item BMQ Specific Score:

Adalimumab For Visit 2, Visit 3, Visit 4, Visit 5, and as appropriate for Early Termination Morisky Medication Adherence Scale (MMAS)

Patient self-reported Medication-taking-Scale: Scoring: high-low;

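### The BMQ scoring text gives no answer key and no reversal for the Necessity items; under any uniform key, opposite belief profiles get the same 10-item Specific total

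*Combined protocol and SAP*

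**What the plan says.** Section 5.1 of the protocol makes the BMQ the instrument for the main objective: "Changes in the Beliefs about Medicines Questionnaire (BMQ) at 12 months compared to baseline", together with correlations between beliefs and adherence. Section 11.1.1 repeats this as the primary end point. Neither names a subscale or a total.

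Section 6.5.1 describes two Specific factors of five items each (Necessity and Concern) and two General factors of four items each (Harm and Overcure). It then describes one total: "score, the sum of all the points from the Specific AND General questions range from 17 (lowest score) to 85 (highest score"). Its direction is given as "Patients who have positive beliefs about medicine have a score < 47 and patients who have negative beliefs have a score > 47". No key, reversal or direction is given for the factors.

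The BMQ form in Appendix D has ten items, all Specific. Items 1-5 are Necessity statements such as "Without my medicines I would become very sick". Items 6-10 are Concern statements such as "Having to take medicines worries me". Every item carries the same options, "a. Strongly disagree b. disagree c. uncertain d. agree e. strongly agree". The form indicates a score from 1 to 5 and ends with one field, "Total 10-item BMQ Specific Score". The letter-to-point key, formula, range and direction of that field are not printed.

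Section 11.2 adds: "A data analysis plan will be available prior to the conduct of the statistical analysis for the study". That plan is not among the supplied documents.

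**The concern.** Agreement with a Necessity item is favourable to the medicine; agreement with a Concern item is unfavourable. Adding the two sets of points without reversing one of them mixes opposite meanings in one number. A patient who becomes more convinced of the need for treatment and less worried about it can then show no change at all. Likewise, if Necessity and Concern relate to adherence in opposite directions, the two relations offset.

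This affects the instrument behind the main objective. Appendix D prints point values for the MMAS, TSQM and RADAI, but only letters for the BMQ. Someone scoring from the printed text would most naturally apply one key to all ten items and add.

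**Working it through.** **Inputs.** Section 6.5.1: 5 Necessity, 5 Concern, 4 Harm and 4 Overcure items; stated range 17-85; cut-off 47; high = negative. Appendix D: 10 Specific items, 1 to 5 points each, options a to e in the same order throughout. No assumed SD, correlation or dropout rate is needed.

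**The stated range.** With 1 to 5 points per item, the range runs from the number of items to five times that number.
- Items described: 5 + 5 + 4 + 4 = 18, giving 18-90.
- A range of 17-85 needs 17 items.
- The printed form has 10 items, giving 10-50.

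So the stated 17-85 fits neither the factors described nor the printed form.

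**Specific total under a uniform key.** Let N and C be the Necessity and Concern sums, each 5-25 when strong agreement earns 5.
- Strong agreement = 5: total = N + C. Full necessity, no concern: 25 + 5 = 30. No necessity, full concern: 5 + 25 = 30.
- Strong agreement = 1: each item becomes 6 - x, so total = (30 - N) + (30 - C) = 60 - (N + C). The first profile gives 5 + 25 = 30 and the second 25 + 5 = 30.

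The tie is not confined to the extremes. With the same answer x on all Necessity items and y on all Concern items, swapping x and y leaves the total unchanged for all 25 pairs, under both keys.

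**Consequence for the main analyses.** With strong agreement = 5 and A for adherence:
- change in total = ΔN + ΔC, so a rise of d in Necessity with a fall of d in Concern gives 0;
- Cov(N + C, A) = Cov(N, A) + Cov(C, A), so terms of opposite sign offset.

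The other uniform key only changes the sign of both expressions.

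**Items 1-5 reversed.** Total = (30 - N) + C = 30 - (N - C), range 10-50, high = negative. The two profiles now score 30 - 20 = 10 and 30 + 20 = 50. The change is ΔC - ΔN, so opposite movements add up, but equal movements in the same direction cancel.

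**Specific-plus-General total, 18 items, General answered consistently with the profile.**
- Strong agreement = 5: favourable 25 + 5 + 8 = 38; unfavourable 5 + 25 + 40 = 70.
- Strong agreement = 1: favourable 5 + 25 + 40 = 70; unfavourable 25 + 5 + 8 = 38, against the stated direction.

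The Specific part is 30 in every case. The whole gap of 32 is 40 - 8, from the General items.

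**The 47 cut-off on the 10-item form.** The maximum is 50, so only totals of 48, 49 and 50 exceed 47. These arise from 55 + 10 + 1 = 66 of the 5^10 = 9,765,625 answer patterns. Both opposite profiles, at 30, would fall on the positive side.

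**The case against.** The strongest reply is that silence is not a rule. Section 6.5.1 adds up points but never says how an answer earns them. Since no uniform key makes all the items agree with the stated direction, an unprinted mixed key may be intended. The scoring may also sit in the data analysis plan or in the instrument's cited source, neither of which was supplied. This stands: a reader might infer that the protocol prescribes an unreversed sum, and the documents do not support that. What they support is that the key and any reversal are unstated, and that the printed form points towards a uniform key.

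Second, the sentence with the 17-85 range defines the Specific-plus-General total, while the tie belongs to the Specific total on the eCRF. This also stands. A reader might infer that the full total ties as well; with consistent General answers it gives 38 against 70. But that separation rests on items absent from the printed form.

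Third, the objectives do not say that a single total will be analysed. True, but they name no alternative, and the only totals the documents describe are these two.

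Two further inferences should be resisted.
- The 47 cut-off might seem to misclassify patients. With 18 items, strong agreement = 5 and Concern and General neutral, denying need gives 5 + 15 + 24 = 44 (positive) and affirming it gives 25 + 15 + 24 = 64 (negative). This is hypothetical unless General items are collected.
- The number of Necessity/Concern pairs that total 30 in the plain sum (21 of 21 × 21 = 441) might seem to favour the reversed total. It does not: the reversed total is 30 whenever N = C, which is also 21 pairs.

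Finally, the study is descriptive and item answers can be rescored. That lowers the cost of repair, but a mean change or correlation of a score that mixes opposite meanings remains hard to interpret.

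**Conclusion.** The point holds for the protocol and eCRF as written. The BMQ key and the treatment of the Necessity items are unstated, and under any uniform key the two fully opposite profiles both score 30 on the 10-item Specific total, against 10 and 50 with items 1-5 reversed. The arithmetic is exact; it is conditional on a uniform key, which the form implies but does not state. It extends to the main analyses only if they use the Specific total.

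No size can be put on the effect on the observed change or correlation, because the documents give no inputs for it. The text allows a real change or association to be hidden; it does not show that one will be. A reversal rule in the data analysis plan would settle the scoring, but section 6.5.1 and the eCRF would still need to state it.

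**What to change.** Before analysis:
1. State one key, a = 1 to e = 5, in section 6.5.1 and on the eCRF.
2. Analyse Specific-Necessity (5-25) and Specific-Concern (5-25) separately, for both the 12-month change and the correlation with adherence.
3. If a single Specific total is also reported, reverse items 1-5 (6 - x), giving 10-50 with high = negative. Note that it equals 30 - (Necessity - Concern) and so hides changes in the same direction; it should not replace the two components.
4. Do not apply the 17-85 range or the 47 cut-off to the 10-item form.
5. Settle whether General items are collected, and make section 6.5.1, the eCRF and the data analysis plan agree. If that plan already holds a scoring rule, copy it into the other two.

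The cost is wording and programming. The items are printed singly on the eCRF, so stored answers can be rescored without new data. The downside is that two scores are reported instead of one, and any totals already entered must be recalculated.

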4.0 Rationale

The aim of this non-interventional post-marketing observational study (PMOS) is to assess RA, PsA, AS, PsO, CD and UC patients' adherence attitudes (beliefs), currently being managed in a specialist rheumatology, dermatology or gastroenterology practice or respective hospital department, to maintenance therapy with a scheduled Adalimumab monotherapy or a combination therapy with methotrexate and to investigate whether there are correlations between such beliefs and adherence to maintenance treatment. For the assessment of RA, PsA, AS, PsO, CD or UC patients attitudes/beliefs to their scheduled maintenance treatment and medicine in general we are going to use the Beliefs about Medicines Questionnaire (BMQ)⁴ at the beginning of this study. In order to identify RA, PsA, AS, PsO, CD or UC patients at risk for non-adherence in due time in the course of this study the Morisky Medication Adherence Scale (MMAS)⁵ shall be used. In this context it is also of interest to evaluate patients' treatment satisfaction during Adalimumab monotherapy or combination therapy with methotrexate for which reason the Treatment Satisfaction Questionaire for Medication (TSQM)^{6,7} is used. As part of clinical practice the laboratory parameters ESR and/or CRP will be measured as an indication for disease activity. Furthermore the degree of disease activity has certainly a significant impact of treatment adherence for which reason the Rheumatoid Arthritis Disease Acitivity Index (RADAI) for RA and if reasonable for PsA patients, the Bath Ankylosing Activity Index (BASDAI) for AS patients, the Psoriasis Area and Severity Index (PASI)^{10,11} for plaque psoriasis, Harvey-Bradshaw Index (HBI)¹² for CD patients and the Partial Mavo score (PMS)¹³ for UC patients shall be used.

P13-562 Protocol

Remark: A patient support program is not offered or scheduled by the sponsor. As this is a noninterventional study all decisions are up to a participating physician. A physician may offer a patient support program to a patient anyhow. As this might affect study results a respective question is incorporated in the eCRF.

Adalimumab \cap

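### Section 6.5.1 states a BMQ range that does not fit its own 18 items, and a combined total and belief classes that cannot be computed from the 10-item form in Appendix D

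*Combined protocol and SAP*

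**What the plan says.** Section 4.0 says that for attitudes to "scheduled maintenance treatment and medicine in general we are going to use the Beliefs about Medicines Questionnaire". Section 5.1 makes the 12-month change in the BMQ, and its correlation with adherence, the main objective. Section 11.1.1 makes beliefs at Visits 1 and 5 the primary end point.

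Section 6.5.1 describes the instrument. The Specific part has two 5-item factors, Necessity and Concerns. For the General part, "The BMQ-General comprises two 4-item factors". For the total score it says that "the sum of all the points from the Specific AND General questions range from 17 (lowest score) to 85 (highest score", and it sets the classes: "Patients who have positive beliefs about medicine have a score < 47 and patients who have negative beliefs have a score > 47".

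The form in Appendix D, for Visit 1, Visit 5 and early termination, is headed "10-item Beliefs about Medicines Questionnaire (BMQ". Its introduction says "We would like to ask you about your personal views about your medicine and medicine in general". It gives each item 1 to 5 points, lists ten statements with the options "a. Strongly disagree b. disagree c. uncertain d. agree e. strongly agree", and ends with one line, "Total 10-item BMQ Specific Score". It contains no General item.

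Section 11.2 calls for a descriptive analysis and promises a data analysis plan, which is not among these documents.

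**The concern.** Two mismatches need to be kept apart. The first is inside Section 6.5.1: the item count and the stated range differ by one item. Alone, that would be a small slip and would not prevent a total from being formed. The second is between Section 6.5.1 and Appendix D: the text defines a combined Specific and General score with two belief classes, but the form collects only the Specific part.

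At stake is whether the score for the main objective is fixed before the analysis. As the documents stand, an analyst could not produce the total or the classes that Section 6.5.1 defines. The analyst would have to fall back on the form's pooled 10-item sum, which adds two subscales that point in opposite directions and for which no reverse scoring is stated.

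**Working it through.** **Inputs**
- Specific items: 2 × 5 = 10 (Section 6.5.1).
- General items: 2 × 4 = 8 (Section 6.5.1).
- Points per item: 1 to 5 (Appendix D, BMQ form).
- Stated total range: 17 to 85 (Section 6.5.1).
- Items on the form: 10, with one Specific total (Appendix D).

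**Formula.** A sum of k items scored 1 to 5 runs from k × 1 to k × 5.

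**Step 1: reproduce the stated range.** 17 / 1 = 17 and 85 / 5 = 17, so 17-85 is the range for exactly 17 items.

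**Step 2: the items described.** 5 + 5 + 4 + 4 = 18, which gives 18 × 1 = 18 to 18 × 5 = 90. Other item scorings do not rescue the stated range: 18 items with a lowest score of 0 or 1 start at 0 or 18, and with a highest score of 4 or 5 they end at 72 or 90.

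**Step 3: the form.** 10 items give 10 × 1 = 10 to 10 × 5 = 50. The General items, worth 8 to 40 points, are absent: 8 / 18 = 44% of the items described. The combined total, and therefore the classes built on it, cannot be formed from these 10 answers.

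**Step 4: the classes.** Below 47 is positive and above 47 is negative. A total of exactly 47 is possible on 17 or 18 items and belongs to neither class. No derivation of 47 is given.

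**Step 5: what the pooled 10-item total can distinguish.** By content, items 1-5 are necessity statements and items 6-10 are concerns. Each subscale runs from 5 to 25.

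| Profile | Agree end scores 5 | Agree end scores 1 |
|---|---|---|
| Strong necessity, weak concerns | 25 + 5 = 30 | 5 + 25 = 30 |
| Weak necessity, strong concerns | 5 + 25 = 30 | 25 + 5 = 30 |

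The total is the same for opposite profiles, whichever end scores 5. The form does not say which end that is. The Morisky Medication Adherence Scale (MMAS) form that follows it does state its mapping: 0 for yes and 1 for no.

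**The case against.** The case for leaving this alone has real content.

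- **The range and cut-off are not used.** No objective, end point or planned analysis refers to 17-85 or to 47, and the analysis is descriptive. This stands, and it limits the harm.
- **The form has its own score.** It gives points per item and a 10-item total, so a 10-50 score exists. Section 6.5.1 may be describing the published instrument rather than the form used. This stands in part: the form can be scored, but the protocol still assigns the study a total and classes that the form cannot supply.
- **The scoring direction is obvious.** Five ordered options after a 1-to-5 score line read naturally as a = 1 to e = 5, and a page break in item 1 may have disturbed the layout. This is fair, so the point is only that the mapping is not explicit. Step 5 does not depend on it.
- **The data analysis plan may settle it.** That is possible, but it cannot be seen here, and the protocol text would still need correcting.
- **Separate subscales are a preference.** They can be computed from the item answers already recorded, so the form need not change. That is also why reporting them costs almost nothing.

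Loss of General items in the PDF extraction is not a plausible explanation. The form calls itself 10-item at both its heading and its total line, and its numbering runs from 1 to 10.

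**Conclusion.** The text is wrong as written and should be corrected before the analysis. The stated range is off by one item (17-85 against 18-90). The combined total and its two classes cannot be computed from the Appendix D form, which lacks 8 of the 18 described items. The cut-off has no derivation and leaves 47 unclassified. The pooled 10-item total cannot separate opposite Necessity and Concerns profiles.

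Four stronger readings might be inferred, and the documents do not support them:
- *The main objective cannot be evaluated.* The 12-month change can be computed from the 10 items once the mapping is stated.
- *The cut-off contradicts the ranges.* 47 lies inside 17-85, 18-90 and 10-50, and it is nowhere described as a midpoint.
- *Nearly all patients would be classed positive on the form.* No section applies 47 to the 10-item score, and nothing in the documents shows how patients will score.
- *Section 6.5.1 holds the only scoring rule.* The form carries its own 10-item total.

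Nor should it be assumed that every planned correlation is available. Section 5.1 asks for correlation with adherence at baseline as well as at 12 months, but the schedule of activities has no MMAS at Visit 1, so the baseline correlation cannot use that scale.

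The conclusion assumes that the Appendix D form is the one used in the live eCRF.

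**What to change.** First confirm from the live eCRF which BMQ items were collected.

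**If only the 10 Specific items were collected:**
- State in Section 6.5.1 and in the data analysis plan that the instrument is the 10-item BMQ-Specific (Necessity 5-25, Concerns 5-25), and give the answer-to-score mapping.
- Delete the 17-85 range, the combined total and the 47 classes.
- Correct the reference to medicine in general in Section 4.0.
- Report 12-month change and correlation with adherence separately for Necessity and Concerns.
- Leave the patient-facing form as it is, including its introduction, so that baseline and month 12 use the same instrument.

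**If General items were also collected:**
- Correct Appendix D, the item count and the range.
- State the mapping and any reverse scoring.
- Justify the 47 cut-off or drop it. If it is kept, assign a class to exactly 47.

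The cost is one eCRF check and some wording, part of which the data analysis plan may already contain. The downside is that there is no BMQ-General result if those items were not collected, and no simple positive/negative percentage if the cut-off is dropped. Section 6.4 estimates that inclusion ends in September 2016 and this version is dated 27 October 2016. If that estimate held, baseline General items can no longer be added.
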